10. BENEFITS

There is no direct benefit to the participants. Knowledge gained from this study may help to identify a psychological treatment target to reduce prescription opioid craving and misuse, and

therefore, psychological treatments to reduce prescription opioid craving can help patient with chronic pain to use pain medication as prescribed or successfully taper the medication as recommended by a doctor. This study also has the potential to inform that other psychological interventions (cognitive and behavioral therapy for pain and mindfulness), which are known to reduce pain catastrophizing, will be effective in improving medication compliance and success of prescription opioid tapering.

11. PRIVACY AND CONFIDENTIALITY

All participant information and specimens are handled in compliance with the Health Insurance Portability and Accountability Act (HIPAA) and privacy policies of Stanford University, Stanford Health Care, and Stanford Children's Health.

Analysis Plan

We will conduct two-way repeated-measures ANOVAs (Condition \times Time) to test whether reductions in pain catastrophizing are associated with decreases in craving, cortisol levels, and psychological distress (depression and anxiety).

If a significant effect of Condition is observed, we will conduct mediation analyses to test whether the intervention's effects on craving are mediated by reductions in cortisol and psychological distress.

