This study will use previously validated two pain catastrophizing protocols (Taub et al, 2017 and Roditi et al, 2009). Briefly, the induction procedures are; first, ask participants to think and write about their past pain flare up episode for 10 minutes and then, read 10 pain catastrophizing statements. Secondly, participants will read a pain catastrophizing statement of their choice out loud while putting their non-dominant hand in a cold water. The reduction procedures are; first, ask participants to think and write about their best pain management case for 10 minutes and then, read 10 pain coping statements. Secondly, participants will read a coping statement of their choice out loud while putting their non-dominant hand in a cold water.

After completing Study 1, the participants will receive instruction about Study 2, which includes daily home practice of coping statement for 7 days (delivered via REDcap system), completing a daily survey for 14 days (5 minutes, delivered via REDcap system), and donate salivary cortisol (at the time of waking up, 30-min after waking up, and 9pm) at Day 1, 7, and 14. The collected salivary cortisol will be mailed to the lab with a pre-stamped envelope and an ice pack.

If patients need to take certain medications (Steroid or Benzodiazepines) within 3 days of a saliva sample collection, saliva samples will not be collected.

Added study 3 (arm 3)-----

Due to the unexpected event of COVID-19 pandemic, the study 3 (arm 3, online only) was added to examine the effect of pain catastrophizing on prescription opioid craving. Participants enrolled in the study 1 and 2 will NOT be allowed to participate in the study 3. Different from study 1 and 2, participants in study 3 do not need to have a lab visit (all remote study tasks).

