Participants will be okay to participate in other clinical trials except for clinical trials including pain self-management or psychological interventions. If a patient is interested in participating in other clinical trials including pain self-managements or psychological interventions, a patient will be informed of two options : the one will be participating in other studies after completing this study for 14 days and the other option will be not to participate in this study.

k. Payments to Participants

Participants will be compensated \$30 for Study 1, \$5 for daily survey for 14 days, \$5 for three at home saliva samples, and \$5 for completion of all study requirement. Therefore, when completing the whole study requirements, a participant receive a total of \$120.

Travel cost will be compensated: \$25 for people living within 60 miles and \$50 for people living beyond 60 miles.

Added for the Study 3, -----

For study 3, participants will be compensated \$25 for completing the baseline tasks (the 30 or 40-min survey, cognitive testing and blood pressure and HR measure), \$60 for completing the short-daily survey and blood pressure ($\$5 \times 12 \text{ days} = \60), and \$10 for completing a 10-min survey and HR measure at day 8, and \$20 for completing the final survey. When completing all the tasks, the participant will receive additional \$5. Therefore, the total compensation is up to \$120 ($=25+60+10+20+5$). Participants will receive check as compensation.

l. Costs to Participants

NA

m. Planned Duration of the Study

Participants will complete (i) the initial 2.5 hour-laboratory experiment (Study 1) and daily home practice of coping statement and daily survey (3-5 minutes, Study 2) for 14 days. (iii) This study estimates 3 years of data collection and 1 year of data analysis.

Added for study 3, -----

Participants will completed (i) the initial 45-60min baseline survey, cognitive testing, and resting blood pressure and HR measure, (ii) a brief daily survey, resting blood pressure and HR measure for 15 days and practicing a 5-min daily coping statement 15 days (only for the 50% of people who are assigned to the coping statement condition), (iii) a 10 min survey at Day 8 and blood pressure and HR measure, and (iv) 20 min-final survey and cognitive testing, and blood pressure and HR measure.

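### Study 2 home cortisol is analysed by a repeated-measures ANOVA that classically needs complete records, although the protocol itself withholds some saliva; a mixed model would use every collected day

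*Combined protocol and SAP*

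**What the plan says.** The Analysis Plan, placed under Section 11, consists of two sentences. The first: "We will conduct two-way repeated-measures ANOVAs", with factors Condition and Time, for craving, cortisol and psychological distress. The second makes mediation conditional: "If a significant effect of Condition is observed, we will conduct mediation analyses", with cortisol and distress as the mediators of any effect on craving. Neither sentence lists the levels of Time, defines an analysis set or says what happens to incomplete records, and no other section does.

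Section 2a sets Study 2 home saliva at three times a day ("at the time of waking up, 30-min after waking up, and 9pm") on Days 1, 7 and 14. It then says that if a participant needs a steroid or benzodiazepine "within 3 days of a saliva sample collection, saliva samples will not be collected". Section 8h excludes daily users of these medicines from Studies 1 and 2, so intermittent users can enrol. Study 3 collects no saliva.

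**The concern.** Classical two-way repeated-measures ANOVA works on a complete person-by-occasion table. A participant lacking one cell is either left out or the procedure will not run. The protocol contains a rule that creates such gaps by design for one outcome. Payment for saliva ("for three at home saliva samples", Section 8k) may limit voluntary loss but cannot prevent samples being withheld by rule.

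Two things are at stake, both confined to Study 2 cortisol and any mediation analysis that uses it:

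- **Precision.** Collected samples are discarded. On a one-day-withheld reading, a person who loses one collection day (three samples) also loses the other 9 - 3 = 6 from the analysis.
- **Bias.** Need for a steroid or benzodiazepine may be related to pain, stress or cortisol. If withholding differs by arm, a complete-case comparison can be distorted.

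A related gap is that Time is undefined. If the nine samples were entered as one Time factor, the within-day cortisol pattern (waking, 30 minutes later, evening) would be mixed with change across days.

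**Working it through.** **No plan figure to reproduce.** Section 8a gives 156 participants without power, effect size, loss rate or split between the in-person and online studies. Every loss rate below is therefore an assumption.

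**Inputs.** From the documents: three home collection days (1, 7, 14), three samples each. Assumed: probability p that a day is collected = 0.98, 0.95, 0.90, 0.85; correlation of cortisol between days r = 0.5; whole-day loss.

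**How many days one use removes.** Collection days are 7 - 1 = 6 and 14 - 7 = 7 days apart, so a single use will normally fall inside the window of one collection day only. This presumes that the rule works day by day, which Section 2a does not state.

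**Share of participants complete on all three days.**
- Independent losses: p³.
- Losses clustered within person (beta-binomial, correlation 0.5): p(p+1)(p+2)/6.

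At p = 0.90: 0.9³ = 0.729, and 0.9 × 1.9 × 2.9 / 6 = 0.826.

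**Collected days discarded by the complete-case analysis (independent losses).** 1 - p². At p = 0.90: 1 - 0.81 = 0.19.

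**SE ratio for the arm difference averaged over days, complete cases against all observed days.** A person with m observed days contributes information 1/[r + (1-r)/m], which is 1.5, 1.333 and 1 for m = 3, 2, 1 at r = 0.5. The ratio is the square root of [sum over m of P(m) × information(m)] / [P(3) × 1.5].

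At p = 0.90, independent: P(3), P(2), P(1) = 0.729, 0.243, 0.027. The numerator is 1.0935 + 0.324 + 0.027 = 1.4445, and √(1.4445/1.0935) = 1.149.

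At p = 0.90, clustered: P(3), P(2), P(1) = 0.8265, 0.0855, 0.0495. The numerator is 1.2398 + 0.1140 + 0.0495 = 1.4033, and √(1.4033/1.2398) = 1.064.

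**SE ratio for Day 14 minus Day 1.** Same comparison, with the mixed-model information summed over all patterns of observed days. At p = 0.90, independent, the share of full-data information kept is 0.729 for complete cases and 0.869 for the mixed model; √(0.869/0.729) = 1.09.

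| Days lost | Complete, independent | Complete, clustered | Collected days discarded, independent | SE ratio, average, independent | SE ratio, average, clustered | SE ratio, Day 14 - Day 1, independent |
|---|---|---|---|---|---|---|
| 2% | 94% | 96% | 4% | 1.03 | 1.01 | 1.02 |
| 5% | 86% | 91% | 10% | 1.07 | 1.03 | 1.04 |
| 10% | 73% | 83% | 19% | 1.15 | 1.06 | 1.09 |
| 15% | 61% | 75% | 28% | 1.24 | 1.10 | 1.14 |

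Varying r from 0.3 to 0.7 changes the 15% independent figures to 1.22-1.25 (average) and 1.14-1.15 (Day 14 - Day 1).

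**Software check.** On simulated data (20 people, three days), one of the 60 person-occasions was deleted. A standard repeated-measures ANOVA routine refused to fit because the data were unbalanced. A mixed model kept all 20 people and 59 observations.

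**The case against.** The strongest reply is that the plan never says incomplete participants will be dropped. That is correct: listwise deletion is inferred from the method named. What stands is that this is how the method classically works and that nothing in the documents replaces it.

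Second, the benefit of a mixed model depends on how the withholding rule is read. If one use means that all of a person's home saliva is withheld, there is no home cortisol to analyse by any method. This limits the claim, and the rule needs clarifying.

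Third, the loss may be small. Daily users are excluded and intermittent use probably clusters within people, so the lower columns of the table may be nearer the truth. At 2% loss the SE ratio is only 1.01-1.03. This stands as to size.

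Fourth, a mixed model removes only bias that observed data explain. Unmeasured stress or pain behind the medication use would affect both analyses. This also stands.

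A reader might infer that the saliva rule damages the craving analysis. It does not: it removes nobody from the craving or distress ANOVAs, which are exposed only through missed surveys or skipped items (Section 2b allows skipping). A reader might also treat the diary ("completing a daily survey for 14 days") as a 14-level Time factor that would lose most participants. At an assumed 90% daily completion that gives 23-72% complete, depending on clustering. But the documents do not say that the diary carries the outcome or that each day is a level.

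**Conclusion.** The point holds for Study 2 home cortisol and for mediation that uses it. The named analysis classically requires complete records, the protocol builds in incomplete ones, and no rule connects the two. With 2-15% of days lost, the complete-case SE for the average arm difference is about 1.01-1.10 times (clustered losses) to 1.03-1.24 times (independent losses) that from all observed days. For Day 14 minus Day 1 with independent losses it is about 1.02-1.15 times. These sizes rest on assumed loss rates, whole-day loss, a between-day correlation near 0.5 and withholding that applies to the affected day only.

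The documents do not support saying that the plan prescribes deletion, that craving or distress results are compromised by the saliva rule, that Study 3 cortisol is affected (none is collected), or that a mixed model would keep every participant. The change is worth making because it is cheap and loses little if few samples turn out to be missing.

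**What to change.** - Replace the ANOVA with a linear mixed model on all observed occasions: condition, day, condition by day, and a person random effect. List the levels of Time for each study and outcome.
- For home cortisol, add sample time within day and a day-within-person random effect (or an equivalent covariance), because three samples share a day. Keep partial sets.
- State in Section 2a whether the withholding rule removes the affected collection day or all of a person's home saliva. The choice is the sponsor's.
- Report by arm the number of samples withheld for steroid or benzodiazepine use.
- Add a sensitivity analysis that shifts withheld values by a stated amount in one arm. For scale, 10% of days withheld with a 0.5 SD shift moves the average difference by 0.10 × 0.5 = 0.05 SD; 15% with a 1 SD shift moves it by 0.15 SD.

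Cost: revised analysis wording and slightly more analysis work, with no new data. The mixed model assumes values are missing at random, so it does not cure loss that depends on unobserved stress, pain or cortisol; hence the sensitivity analysis. If outcome data have already been seen, the change should be labelled post hoc.

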1. PURPOSE OF THE STUDY

a. Brief Summary

Adherence to prescription opioid and opioid tapering as indicated are critical for safe chronic opioid therapy for chronic pain, but this can be difficult for patients experiencing prescription opioid craving.

Because pain catastrophizing is proposed as a possible treatment target by our and others' preliminary results, the proposed study aims to determine whether pain catastrophizing is a treatment target to reduce prescription opioid craving and to investigate whether negative affect and stress hormones are potential mediators.

b. Objectives

We hope to learn whether a psychology intervention to lower pain catastrophizing will reduce opioid craving, and whether psychological and physical distress will be potential mediators of the treatment effect.

c. Rationale for Research in Humans

The purpose of this study is to examine the effect of a psychological intervention on opioid craving and medication misuse in patients taking prescription opioid for pain management.

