Participant in the study 3 will do the baseline survey and be randomized into two conditions: daily coping statement practice (50%) and no coping statement (50%). The participants in the daily coping condition will be asked to choose the coping statement of the day and rehearse throughout the day for the 15 days. Except this difference, participants in the both conditions will do a daily survey and check the resting HR for five minutes for the 15 days. The participant will receive a wrist heart rate device (i.e., a heart rate measuring device) before the baseline survey and heart rate will be anonymously collected. Also, participants in the both conditions will do a cognitive testing at day 1 (baseline), day 8, and day 15 (final study). Different from the study 1 and 2, study 3 will examine resting sympathetic cardiac levels and cognitive function as a mediator of the effect of the pain catastrophizing on craving.

Stanford is the only study site, University of Oklahoma will only conduct EDTA sample analysis

b. Procedure Risks

All members of the study team have been trained to conduct the research procedures in the safest manner possible. There are no known risks to complete the study procedures as all the procedures and questionnaires are validated in this patient population and this medical setting. However, patients may feel temporarily uncomfortable for blood draw, laboratory pain testing, and completing some questionnaires. To minimize the risk, we will exclude patients with a needle phobia and history of vasovagal syncope for blood draw. Additionally, vital signs will be assessed prior to the blood draw and throughout

the laboratory procedures. During the informed consent procedure, the patients will be informed that they can withdraw their consent anytime without penalty and their time will be compensated. Patient will have an option to not to answer any questions that make them feel uncomfortable. Finally, we will obtain the certificate of confidentiality to protect the privacy of research subjects by prohibiting disclosure of identifiable, sensitive research information to anyone not connected to the research except when the subject consents or in a few other specific situations.

c. Use of Deception in the Study

The exact study hypothesis and study procedures of part 1 are not completely described in the consent, but will be debriefed at the end of Experiment 1. **Use of Audio and Video Recordings**

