3. BACKGROUND

a. Past Experimental and/or Clinical Findings

Chronic pain and opioid overdose are two critical public health problems in the US. About 25 million adults (11%) suffer from chronic daily pain and up to 8 million use opioids to manage chronic pain. Unfortunately, 46 people die daily from overdose of prescription opioids. For safe chronic opioid therapy for chronic pain, physicians monitor patients' adherence to prescription opioids, and reduce or discontinue the prescription as indicated. Yet, adherence and cessation are not easy for some patients and one reason is opioid craving, a strong desire or urge to use opioids. Our preliminary data show about 34% of patients on chronic opioid therapy report craving. Craving is strongly associated with opioid misuse and negative health outcomes. To date, we do not fully understand the underlying mechanisms of prescription opioid craving in chronic pain sufferers, and psychological treatment targets to reduce craving. Based on our pilot survey, patients endorsing craving reported greater pain catastrophizing than those endorsing no craving. Our other survey study also reported a positive link between pain catastrophizing and opioid craving in patients on chronic opioid therapy for chronic pain conditions. Although these findings propose a possibility that lowering pain catastrophizing may decrease opioid craving, cross-sectional observational studies are limited in investigating a causal association. Potentially, pain catastrophizing enhances stress-induced opioid

craving because stress-induced opioid craving is a well-established phenomenon in studies of addiction, and pain catastrophizing is associated with greater pain and emotional distress in patients with chronic pain. Therefore, the proposed project seeks to determine: a) the effect of pain catastrophizing on prescription opioid craving in patients on chronic opioid therapy for chronic pain and b) psychological (negative affect) and physiological (cortisol, norepinephrine) distress as potential mediating variables.

Findings from Past Animal Experiments

NA

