h. Eligibility Criteria

i. Inclusion Criteria

For study 1, 2, and 3,

1. At least 18 years old
2. Chronic opioid therapy at least 3 months
3. Any chronic pain conditions at least 3 months

ii. Exclusion Criteria

For study 1 and 2,

1. Current diagnosis of cancer
2. Other severe psychiatric and cognitive conditions (schizophrenia, delusional disorder, psychotic disorder, dementia, Parkinson's or dissociative disorder)
3. An skin conditions on the non-dominant hand (pain testing site)
4. Non-English speaker
5. No access to email or smart phone
6. (For saliva collection) Daily use of cortisol or benzodiazepines
7. Being pregnant
8. Needle phobia for blood draw
9. Current suicide thoughts

added for study 3-----

For study 3,

1. Current diagnosis of cancer
2. Other severe psychiatric and cognitive conditions (schizophrenia, delusional disorder, psychotic disorder, dementia, Parkinson's or dissociative disorder)
3. Non-English speaker
4. No access to email or smart phone
5. Being pregnant
6. Current suicide thoughts
7. Concurrent psychological treatments during the 15-day study period.

i. **Screening Procedures**

New recruitment method will be used, the Research Participant Engagement Program (RPEP). RPEP will use coded diagnoses and procedures, clinical records, demographics with embedded identifiers, medications, names, telephone numbers, home address, date of birth, date of service, date of diagnosis, emails, and MRNs to recruit via postal mail.

Potentially eligible patients will complete an online prescreening survey. The online screening survey will assess patients' chronic pain and other health conditions, pain medication use, and prescription misuse, and craving. For prescription misuse and craving, the PROMIS item bank for the misuse of prescription pain medication and the COMM will be administered. This study will invite people endorsing chronic pain at least 3 months, taking opioid pain medications at least 3 months, and no craving or craving at any frequency on the PROMIS craving item (i.e., I experienced cravings for pain medication). Name, email, and phone number will be collected to invite eligible participants for the study.

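### The gate for mediation does not name its deciding test, and either term of the unadjusted ANOVA is usually less powerful than a contrast adjusted for baseline craving

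*Combined protocol and SAP*

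**What the plan says.** The Analysis Plan is two sentences long. The first sets the model, "We will conduct two-way repeated-measures ANOVAs", with factors Condition and Time, and the purpose, "to test whether reductions in pain catastrophizing are associated with decreases in craving", with cortisol and psychological distress as further outcomes. The second sets the gate: "If a significant effect of Condition is observed, we will conduct mediation analyses". No covariate, level of Time, baseline value or significance level is given.

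Other sections bear on this:
- Section 1b makes mediation an objective: "whether psychological and physical distress will be potential mediators of the treatment effect".
- Section 2a (Study 3) places a survey before allocation: "Participant in the study 3 will do the baseline survey and be randomized into two conditions". Whether it measures craving is not stated.
- Section 2a (Study 2) has participants "completing a daily survey for 14 days". Whether the survey covers craving is not stated.
- Section 8, Screening Procedures, admits people with "no craving or craving at any frequency on the PROMIS craving item". The item is part of the screening survey, but the analysis gives it no role.
- Section 3a reports preliminary data in which "about 34% of patients on chronic opioid therapy report craving".

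**The concern.** The first sentence speaks of decreases, which points to the Condition-by-Time interaction. The second names Condition, which read literally is the main effect. The same data could open or close the gate depending on which term is chosen, and nothing fixes that choice before the data are seen. A stated objective depends on it.

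Both terms also have a power problem. The main effect keeps stable between-person differences in craving in its error and, if baseline is a level of Time, averages the effect with a point where none can exist. Enrolling people without craving alongside people with it widens those differences. The interaction removes them, but with many daily values it has many degrees of freedom, and a sustained effect is spread across all of them.

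**Working it through.** **Inputs.** From the documents: 156 participants (Section 8a); three conditions in Study 1, two in Study 2, two at 1:1 in Study 3 (Section 2a); 34% craving in preliminary data (Section 3a). The 156 cannot be reproduced, because no alpha, power, effect size or SD is given. Assumed: two-sided 0.05; SD 1; effect d = 0.5 in people who crave; people who do not crave stay at zero; cravers' mean μ of 1.5 to 3 SD; correlation ρ of 0.3 to 0.7; n = 78 per arm. The last is an upper bound, since it puts all 156 in one two-arm comparison.

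**Formulas** (k post-baseline values, constant effect, equal correlations, v = (1+(k−1)ρ)/k):
- Main effect, baseline as a level of Time: effect dk/(k+1), variance (1+kρ)/(k+1).
- Post mean minus baseline (1 df): effect d, variance v+1−2ρ. This equals the interaction only when k = 1.
- Baseline-adjusted post mean (ANCOVA): effect d, variance v−ρ².
- Noncentrality = effect/√(2·variance/n); critical t about 1.975.

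**One post value, all crave, ρ = 0.5**
- Main effect: 0.25/√(2×0.75/78) = 1.80, power 43%.
- Interaction: 0.5/√(2×1/78) = 3.12, power 87%.
- Adjusted: 0.5/√(2×0.75/78) = 3.61, power 95%.

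Simulation gives 44, 86 and 94%. The main effect's efficiency relative to the adjusted contrast is (1−ρ)/2, below one half for any ρ > 0.

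**One post value, 34% crave, ρ = 0.5**
- The arm difference falls to 0.34×0.5 = 0.17, or 0.085 once averaged with baseline.
- Main effect, μ = 1.5: variance 0.34×0.75 + 0.34×0.66×(1.5²+1.25²)/2 = 0.683; noncentrality 0.64; power about 10%. With μ = 3 the variance is 2.11 and power about 6%. Simulated range 5–10%.
- Interaction: variance 0.34 + 0.34×0.66×0.5²/2 = 0.368; noncentrality 1.75; power 41%.
- Adjusted: 46–50% by simulation.

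Over ρ = 0.3 to 0.7 and 52 per arm, the simulated ranges are 6–8, 23–44 and 25–51%.

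**Fourteen daily values, all crave, ρ = 0.3**
- Main effect: 0.467/√(2×0.347/78) = 4.95, power nearly 100%.
- Post mean minus baseline and the omnibus interaction share one noncentrality, (78/2)×0.5²×(14/15)/0.7 = 13.0. On 1 df (√13 = 3.61) that gives 95%; on 14 df it gives about 60%.

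Simulated power with 14 values, ρ = 0.3 to 0.7, equal correlations:

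| Share craving | Main effect | Omnibus interaction | Post mean minus baseline (1 df) | Adjusted |
|---|---|---|---|---|
| 34% | about 11–29% | about 17–39% | 52–84% | about 64–94% |
| All | 92–100% | about 60% at ρ = 0.3 | 95–100% | about 100% |

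With 75% craving, μ = 1.5 and ρ = 0.3, the interaction has about 43% and the main effect about 80%.

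**Sensitivity**
- No mixture of cravers and non-cravers: where the adjusted contrast has 80% power, the main effect with baseline as a level has 38, 29 and 19% (k = 1) or 62, 48 and 32% (k = 14) at ρ = 0.3, 0.5 and 0.7. The loss does not depend on the 34%.
- AR(1) correlation, k = 14, no mixture: the main effect's relative efficiency is 0.92, 0.90 and 0.84. With 75% craving the powers are 82–92% against 98–99%; with 34%, 10–33% against 51–70%.
- Under no effect, the main effect and the adjusted contrast reject about 5% of the time.
- Against an adjusted test of the last day alone, the 14-day main effect can be stronger (relative efficiency 1.22 at ρ = 0.5, constant effect).

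**The case against.** The plan never says main effect. Its gate sentence goes on to speak of the intervention's effects on craving, so the phrase may mean any effect of the intervention. The lowest figures need several assumptions together: the literal reading, baseline averaged in, a single later value, 34% craving, and non-cravers fixed at zero. The 34% comes from preliminary data, not from this trial's intake. Studies 2 and 3 have daily surveys, and if everyone craves and craving is measured daily the main effect is adequate. Preferring ANCOVA improves power; it does not correct an invalid test.

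All of that stands as a limit on size. It does not supply the missing deciding term, time points or baseline role.

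Three stronger readings are tempting, and the documents support none of them:
- That the gate is set on the main effect. The wording is ambiguous, and decreases points the other way.
- That the gate is too easy to pass. The loss is in power, not false positives.
- That naming the Condition-by-Time interaction would settle it. That is nearly so with one later value. With daily values the omnibus interaction falls well short of the adjusted contrast at 34% craving, and can fall below the main effect.

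**Conclusion.** The point holds as an unspecified gate with a usually avoidable loss of power. How large the loss is in this trial cannot be fixed from the documents. In the scenarios run it ranges from negligible (all crave, 14 daily values, main effect) to severe (34% crave, one later value, main effect 5–10% against 46–50% adjusted). On the same post-baseline data, the baseline-adjusted contrast was never less powerful than either ANOVA term. Usually is the right word: the main effect's loss is small under AR(1) correlation once most participants crave, and the advantage can reverse if the adjusted contrast uses only the last day. The change should be made, because it costs little and removes a choice otherwise open after the data are seen.

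**What to change.** For each reduction-versus-control comparison, test post-baseline craving, taken as the mean of the daily values where craving is measured daily, adjusted for craving measured before that study's randomisation. Where no such baseline exists, adjust for the screening craving item in its graded form.

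Replace the effect-of-Condition wording with this adjusted contrast as the gate for mediation. Name the study or studies it applies to, its significance level and the time points used. State separately how the Study 1 induction-versus-control contrast is handled.

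The cost is SAP wording, slightly more analysis work, and linking the screening response to the study ID where it is used. No new participants or measurements are needed. Adjustment does not undo the dilution from participants with little craving to reduce.
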